8.1.2.4 Investigator Brochure Availability

The current versions of the IBs for the agents will be accessible to site investigators and research staff through the PMB Online Agent Order Processing (OAOP) application. Access to OAOP requires the establishment of a CTEP Identity and Access Management (IAM) account and the maintenance of an “active” account status and a “current” password. Questions about IB access may be directed to the PMB IB coordinator via email.

9. BIOMARKER, CORRELATIVE, AND SPECIAL STUDIES

9.1 Integral Laboratory or Imaging Studies

None.

9.2 Integrated Studies

9.2.1 Evaluate tumor for presence of *TAZ-CAMTA1* gene fusion by fluorescence in-situ hybridization.

9.2.1.1 FISH for *TAZ-CAMTA1* gene fusion

The presence of *TAZ-CAMTA1* gene fusion may be detected by fluorescence in situ hybridization (FISH) or polymerase chain reaction. FISH probes have been developed using a red fluorophore to the 5' end of *TAZ* (*WWTR1* gene) and a green fluorophore to the 3' end of *CAMTA1* gene. Cells containing translocation of *TAZ* (*WWTR1*) on chromosome 3 with *CAMTA1* on chromosome 1 can be detected by fusion of the red and green fluorescent signals in nuclei. After processing tissue for FISH, at least 50 nuclei will be examined. Tumor with at least 10% of the nuclei containing a fused signal will be scored as containing the *TAZ-CAMTA1* translocation.

9.2.1.2 Collection of Specimen(s)

The registering site should submit the required specimen for FISH within 2 weeks of patient registration/enrollment. Formalin-fixed, paraffin-embedded archival tumor tissue may be submitted for FISH analysis. Tissue may be from core needle biopsy or excision of an EHE lesion. An adequate amount of tissue should be available to produce 12 slides containing 4 micron thick sections of tumor tissue for FISH and at least 1 slide for hematoxylin and eosin staining. Sites may submit 1 H&E stained slide of representative tumor tissue and either 12 slides containing four micron-thick unstained tumor sections or a paraffin block containing tumor tissue. Unstained sections should be placed on charged

slides and NOT baked.

9.2.1.4 Site performing integrated study

Cleveland Clinic CLIA-certified FISH laboratory

9.3 Exploratory/Ancillary Correlative Studies

9.3.1 Plasma Connective Tissue Growth Factor (CTGF) Level

Plasma CTGF levels may be a useful biomarker of EHE survival as CTGF is a secreted protein whose gene is an immediate downstream target of TAZ-CAMTA1 (Tanas et al., 2016). CTGF is secreted and binds to α IIb β 3 integrin on the cell surface, leading in an autocrine fashion to downstream activation of RAS and MAP kinase pathways. This signal transduction pathway drives TAZ-CAMTA1-mediated NIH/3T3 cell transformation. Inhibition of any portion of this pathway inhibits transformation.

Preliminary studies have shown that CTGF is produced at high levels and secreted into culture media by cells that express TAZ-CAMTA1. CTGF is expressed in human EHE as demonstrated by anti-CTGF western blot of patient tumor lysates. CTGF is secreted by EHE and can be quantified in plasma from EHE patients using standard ELISA. Fibrogen (San Francisco) has supplied a CTGF-specific monoclonal antibody to CTGF that performs well in ELISA. If trametinib results in EHE cell death and objective tumor response, we hypothesize that CTGF plasma levels will decline. Alternatively, if trametinib blocks growth of EHE by inhibiting MEK but does not result in cell death, we expect CTGF plasma levels will remain unchanged.

9.3.1.1 Collection of Specimen(s)

Samples (3-5 mL blood) will be obtained prior to treatment, after 4 weeks and 6 months (in patients with stable or better disease) of treatment, at the time of objective tumor response and upon determination of EHE radiologic or clinical progression.

9.3.1.2 Handling of Specimens(s)

Blood will be drawn in sodium or potassium-EDTA collection tubes and processed

within 60 minutes of collection. After collection of blood into collection tubes, the tubes should be gently inverted 4-6 times to ensure proper mixing of blood with EDTA. The tubes should be centrifuged at 1,000 – 2,000 x gravity at 4 degrees centigrade for 15-20 minutes to separate plasma. After centrifugation, 1-2 mL of plasma should be removed using a clean pipet and placed into two 1.5 mL Eppendorf (or similar) collection vials, labeled with the date of collection, patient ID and study ID or similar specimen tracking information and immediately frozen at -80°C. Specimens should be stored frozen at -80°C or colder until shipped on dry ice.

9.3.1.3 Shipping of Specimen(s)

Samples should be batched for shipping. The site may batch all aliquots from each time point from each study participant in one shipment to avoid unnecessary shipping expense. Samples must be kept frozen and shipped on dry ice via overnight delivery service for arrival to the laboratory on Monday through Friday. Samples should not arrive on Saturday, Sunday or recognized Federal holiday. Samples should be sent to:

[name]
Biopathology Center
Nationwide Children's Hospital
[name]
[name]
[contact]

Notification of shipment should be sent to SARC RPM at [name]

9.3.2 Assessment of MAP kinase pathway signaling

In pre-clinical studies, NIH/3T3 cells stably expressing the *TAZ-CAMTA1* gene fusion were grown in suspension and the MAPK pathway was examined. NIH/3T3 cells containing empty vector were used as control. Phospho-ERK, which is emblematic of MAPK pathway activation was sustained in TAZ-CAMTA1 expressing cells while cells expressing vector alone lost ERK phosphorylation over time. This suggests that TAZ-CAMTA1 maintained MAPK activation. Furthermore, phospho-ERK has been detected in protein lysates of snap-frozen EHE tumor samples and localized phospho-ERK in EHE tumor cells by immunohistochemistry with a phospho-specific anti-ERK antibody which demonstrated strong activation specifically in tumor cells. We hypothesize that tumor responses to clinically administered doses of trametinib will be accompanied by suppression of the MAPK pathway signaling.

Formalin-fixed paraffin-embedded samples will undergo quality review by the SARC SPORE Pathology core and tumor tissue will be analyzed for ERK phosphorylation by

semi-quantitative immunohistochemistry using phospho-ERK (Thr202/Tyr204)-specific antibody (Cell Signaling #4370) and quantitative immunochemistry by AQUA. If ERK is no longer suppressed in tumor progression, MEK 1/2 will be sequenced to identify genetic mechanisms of resistance. Frozen tumor tissue will be reserved for primarily for protein studies of intracellular protein kinase signaling studies, if needed. For example, if IHC suggests that ERK is inhibited, then the snap frozen tissue will be used to make protein lysates for phospho-proteomic arrays (R&D systems) which will provide a panel of anti-phospho-protein antibodies targeting proteins involved in a variety of intracellular signaling pathways to identify activation of alternative signaling pathways that mechanistically could drive progression.

9.3.2.1 Collection of Specimens

Optional tumor biopsy will be performed prior to starting trametinib and after approximately 4 weeks of trametinib treatment (+/- 7 days), and upon progression in patients who previously had objective tumor response. It is encouraged that biopsies be performed to collect tumor tissue for correlative research studies to evaluate the effect of trametinib on MEK signaling. Patients will be provided the option of participating in biopsy of tumor prior to treatment and on treatment with trametinib. If treatment is interrupted in a patient, the biopsy should be delayed until drug is restarted and taken daily for at least 7 days. At a minimum, biopsy should consist of 4 core biopsies using 14 to 16 gauge needles at least 8-10 mm in length. Two core biopsies should be immediately placed in formalin and processed using standard methods in paraffin for standard immunohistochemistry. The remaining cores should be immediately flash frozen in liquid nitrogen or embedded in OCT (optimal cutting temperature) compound and frozen at -80 degrees Celsius.

9.3.2.2 Handling of Specimens

Paraffin-embedded samples should be labeled with date of biopsy, subject ID and Study ID and kept at ambient temperature. Tissue frozen in liquid nitrogen should be kept frozen in an Eppendorf (or similar) clean collection vial labeled with the date of biopsy, subject ID and study ID and stored at -80 degrees Celsius until shipped to Cleveland Clinic on dry ice.

9.3.2.3 Shipping of Specimens

Paraffin-embedded samples should be shipped at ambient temperature. Frozen samples may be batched for shipping. The site may batch all frozen tissue biopsies from each time point from each study participant in one shipment to avoid unnecessary shipping expense. Samples must be kept frozen and shipped on dry ice via overnight delivery service for arrival to the laboratory on Monday through Friday. Samples should not arrive on Saturday, Sunday or recognized Federal holiday. Samples should be sent to:

[name]
Biopathology Center
Nationwide Children's Hospital
[name]

[name]

Notification of shipment should be sent to SARC RPM at [name]

9.4 Special Studies

9.4.1 Tumor Volume

9.4.1.1 Measure: Change in volume of EHE on treatment with trametinib. In a retrospective analysis, a change in tumor volume identified more patients than RECIST 1.1 with response and correlated with survival in a prospective trial of Ewing sarcoma treated with anti-insulin-like growth factor. We will assess changes in tumor volume over time, compare this to response by RECIST 1.1 criteria and correlate with survival. An increase in tumor volume of 100% or more will be scored as progression and decrease in volume of 45% or more will be scored as response.

9.4.1.2 Assessment

9.4.1.2.1. Sites of tumor will be imaged by CT or MRI using standard protocols.

9.4.1.2.2. Imaging tumor will occur within 30 days prior to starting drug, after cycles 2, 4 and 6 and thereafter approximately every 12 weeks. For patients with evidence of disease progression prior to enrollment, CT or MRI scans documenting progression will also be reviewed.

9.4.1.3 Data Recording

9.4.1.3.1. The TRIAD software anonymizes, encrypts and validates the images as they are transferred. Site staff who submit images through TRIAD will need to be registered with the Cancer Therapy Evaluation Program (CTEP) and have a valid and active CTEP Identity and Access Management (IAM) account. Please refer to CTEP Registration Procedures of the protocol for instructions on how to request a CTEP-IAM account. To submit images, the site TRIAD user must be on the site's affiliate rosters and be assigned the TRIAD site user role on the CTSU roster. Users should contact the site's CTSU Administrator of Data Administrator to request assignment of the TRIAD site user role. After the user receives a CTEP-IAM account with proper user role, he/she will need to have the TRIAD application installed on his/her workstation to be

able to submit the image files. TRIAD installation documentation can be found at the link <https://triadinstall.acr.org/triadclient/>. This process can be done in parallel to obtaining the CTEP-IAM account username and password. If you have questions regarding this information, please send an email to the TRIAD Support mailbox at [contact]. For support with the TRIAD application, please send an email to [contact]. Participating sites that are unable to use or access TRIAD may submit digital images through QARC's secure FTP site or in DICOM files on CD/DVD. For questions regarding diagnostic imaging submission, please contact [contact] or [contact].

- 9.4.1.3.2. Timing of Recording. Sites will submit images of CT or MRI obtained prior to starting trametinib within 4 weeks after enrollment. Sites will submit images of CT or MRI performed during the treatment period within 4 weeks of completion of the radiology scan.

10. STUDY CALENDAR

Baseline evaluations are to be conducted within 2 weeks prior to patient registration. Tumor imaging, cardiac evaluation and ophthalmology evaluations must be done within 30 days prior to patient registration. In the event that the patient's condition is deteriorating, laboratory evaluations should be repeated within 48 hours prior to initiation of the next cycle of therapy. The window for cycle visits is +/- 7 days.

	Pre-Study	Wk 1	Wk 2	Wk 3	Wk 4	Wk 5	Wk 6	Wk 7	Wk 8	Wk 9	Wk 10	Wk 11	Wk ⁱ 12	Off Treatment
Trametinib Daily		A	A	A	A	A	A	A	A	A	A	A	A	
Informed consent	X													
Archival tumor tissue sent for TAZ-CAMTA1 FISH	X													
Demographics	X													
Medical history	X													
Concurrent meds	X	X-----									X			
Physical exam	X	X		X		X				X				X
Vital signs	X	X				X				X				X
Height	X													
Weight	X	X				X				X				X
Performance status	X	X				X				X				X
CBC w/diff, plts	X	X		X		X				X				X
Serum chemistry ^a	X	X		X		X				X				X
ESR, CRP ^b	X					X								
Plasma collection for CTGF ^b	X					X								
EKG	X													
Echocardiogram or MUGA ^c	X													Every 12 weeks (+/- 14 days) (use same methodology for baseline and follow up).
Ophthalmology exam ^d	X													
Adverse event evaluation		X-----									X			X
Tumor measurement ^e	X													X
Radiologic evaluation ^f	X													X
Pregnancy test ^g	X													
Optional fresh biopsy of tumor	X				X									
NIH PROMIS Questionnaire ^h	X				X									

A: Trametinib: Dose as assigned; to be taken daily

a: Comprehensive metabolic panel. The panel should include albumin, alkaline phosphatase, total bilirubin, bicarbonate, BUN, calcium, chloride, creatinine, glucose, potassium, total protein, SGOT [AST], SGPT [ALT], sodium.

b: Biomarker assessment: ESR-westergren method preferred and CRP, to be performed by local lab prior to therapy, after 4 weeks and 6 months of treatment (for patients with stable for better disease), at time of objective response and at progression. Plasma for

- determination of CTGF level to be obtained at the same time points and sent to central lab for analysis.
- c: The same modality (ECHO or MUGA) should be used at baseline and at follow-up
- d: Ophthalmology exams should be obtained at baseline, and if clinically indicated, during study. Ophthalmology exam should include Ocular Coherence Tomography, fundoscopy, tonometry, visual field examination, and corrected visual acuity assessments.
- e: Tumor digital files to be sent to QARC for tumor volume assessment.
- f: Tumor measurements do not need to be repeated if patient ends treatment because of documented tumor progression by imaging.
- g: Blood or urine pregnancy test (women of childbearing potential).
- h: NIH PROMIS global health, pain intensity, interference and behavior short form inventories to be obtained prior to trametinib treatment, after 1 month and 6 months of treatment, and on evidence of disease progression or response.
- i: For patients remaining on treatment after week 12, evaluations will include physical exam, weight, performance status, complete blood count with differential and platelet count, and serum chemistry at least once per cycle.

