There have been few clinical trials that have prospectively investigated drug therapies for patients with EHE. For example, a phase II study evaluated bevacizumab in seven patients with locally advanced or metastatic EHE (Agulnik et al., 2013). Two patients had a partial response and four patients demonstrated stable disease with one patient experiencing progressive disease at first evaluation. The mean number of cycles received was 17.3 (52 weeks). Median PFS was 39.1 weeks and median OS was 142.6 weeks. Given the small number of patients in this study, further conclusions cannot be made.

A phase II study by the French Sarcoma Group evaluated the efficacy of sorafenib (800 mg daily) in 15 patients with progressive EHE with a primary endpoint of 9-month PFS (Chevreau et al., 2013). Twelve patients had metastatic disease at the time of enrollment. The 2-month, 4-month, 6-month and 9-month progression free rates were 84.6%, 46.4%, 38.4% and 30.7%, respectively. Median follow-up was 12 months, with a median PFS of 6 months. Median overall survival was not reached at the time of analysis. Two partial responses were noted and lasted 2 months and 9 months. The median treatment duration was 124 days with seven patients requiring dose reductions or transient treatment discontinuation due to toxicity including hand-foot syndrome, diarrhea and mucositis with anorexia. Previously reported treatment and trials have used chemotherapy, immunotherapy, multi-kinase inhibitors or anti-vascular endothelial growth factor inhibitors with marginal benefit; therefore, standard drug therapy for patients with locally advanced or metastatic unresectable EHE has not been established.

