5.5 Duration of Therapy

In the absence of treatment delays due to adverse event(s), treatment may continue for 52 cycles or until one of the following criteria applies:

- Disease progression per RECIST,
- Clinical progression,
- Intercurrent illness that prevents further administration of treatment,

- Unacceptable adverse event(s),
- Patient decides to withdraw from the study
- Pregnancy
 - All women of child bearing potential should be instructed to contact the investigator immediately if they suspect they might be pregnant (e.g., missed or late menstrual period) at any time during study participation.
 - The investigator must immediately notify CTEP in the event of a confirmed pregnancy in a patient participating in the study.
- General or specific changes in the patient's condition render the patient unacceptable for further treatment in the judgment of the investigator.

Patients with clinical progression or disease progression per RECIST who are benefitting from trametinib in reduction of tumor-related symptoms may continue on treatment with trametinib after discussion with the Study PI and CTEP Medical Monitor and approval.

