6.1.7 Trametinib Dose Modification for Reduced Left Ventricular Ejection Fraction

Decreases of the left ventricular ejection fraction (LVEF) have been observed in patients receiving trametinib. Therefore, ECHO/MUGAs must be performed in regular intervals outlined in the Study Calendar. The same procedure (either ECHO or MUGA, although ECHO is preferred) should be performed at baseline and at follow-up visit(s).

Trametinib Dose Modification Guidelines and Stopping Criteria for LVEF Decrease		
Clinic	LVEF-drop (%) or CTCAE grade	Action and Dose Modification
Asymptomatic	Absolute decrease of >10% in LVEF compared to baseline and ejection fraction below the institution's LLN.	
 Interrupt trametinib and repeat ECHO/MUGA within 2 weeks.^a If the LVEF recovers within 4 weeks (defined as LVEF \geqLLN and absolute decrease \leq10% compared to baseline): 
 Consult with the CTEP trametinib medical monitor and request approval for restart. Restart treatment with trametinib at reduced dose by one dose level.^b Repeat ECHO/MUGA 2, 4, 8, and 12 weeks after re-start; continue in intervals of 12 weeks thereafter. If LVEF does not recover within 4 weeks: 
 Consult with cardiologist. Permanently discontinue trametinib. Report as SAE Repeat ECHO/MUGA after 2, 4, 8, 12, and 16 weeks or until resolution. Consult with the CTEP trametinib medical monitor.^c
Symptomatic^b	
 Grade 3: resting LVEF 39-20% or $>20\%$ absolute reduction from baseline Grade 4: Resting LVEF $\leq 20\%$. 	
 Permanently discontinue trametinib. Report as SAE. Consult with cardiologist. Repeat ECHO/MUGA after 2, 4, 8, 12, and 16 weeks or until resolution.

^a If ECHO/MUGA does not show LVEF recovery after 2 weeks, repeat ECHO/MUGA 2 weeks later.

^b Escalation of trametinib to previous dose level can be considered if LVEF remains stable for 4 weeks after restarting of trametinib. Approval from the CTEP trametinib medical monitor is required.

^c Symptoms may include: dyspnea, orthopnea, and other signs and symptoms of pulmonary congestion and edema.

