6.1.9 Trametinib Dose Modification for Hypertension

Increases in blood pressure (BP) have been observed in patients receiving trametinib. Recommendations for BP monitoring and management are provided below.

Monitoring: All BP assessments should be performed under the following optimal conditions:

The subject has been seated with back support, ensuring that legs are uncrossed and flat on the floor.

The subject is relaxed comfortably for at least 5 minutes.

Restrictive clothing has been removed from the cuff area, and the right cuff size has been selected.

The subject's arm is supported so that the middle of the cuff is at heart level.

The subject remains quiet during the measurement.

In subjects with an initial BP reading within the hypertensive range, a second reading should be taken at least 1 minute later, with the two readings averaged to obtain a final BP measurement. The averaged value should be recorded in the eCRF.

Persistent hypertension is defined as an increase of systolic blood pressure (SBP) $>$ 140 mmHg and/or diastolic blood pressure (DBP) $>$ 90 mmHg in three consecutive visits with blood pressure assessments from two readings as described above. Visits to monitor increased blood pressure can be scheduled independently from the per-protocol visits outlined in the study calendar. Ideally, subsequent blood pressure assessments should be performed within 1 week.

Management and Trametinib Dose Modification for Hypertension		
Event	Management Guideline	Dose Modification
Definitions used in the table:		

 - Persistent hypertension: Hypertension detected in two separate readings during up to three subsequent visits. - Well-controlled hypertension: Blood pressure of SBP \leq140 mmHg and DBP \leq90 mmHg in two separate readings during up to three subsequent visits. - Symptomatic hypertension: Hypertension associated with symptoms (e.g., headache, light-headedness, vertigo, tinnitus, episodes of fainting or other symptoms indicative of hypertension) that resolve after the blood pressure is controlled within the normal range. - Asymptomatic hypertension: SBP $>$140 mmHg and/or DBP $>$90 mmHg in the absence of the above symptoms. 		

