(Scenario A) 
 - Asymptomatic and persistent SBP of \geq140 and $<$160 mmHg, or DBP \geq90 and $<$100 mmHg, or Clinically significant increase in DBP of 20 mmHg (but still below 100 mmHg). 	
 • Adjust current or initiate new antihypertensive medication(s). • Titrate antihypertensive medication(s) during the next 2 weeks to achieve well-controlled BP. If BP is not well-controlled within 2 weeks, consider referral to a specialist and go to scenario (B). 	Continue trametinib at the current dose.
(Scenario B) 
 - Asymptomatic SBP \geq160 mmHg, or DBP \geq100 mmHg, or Failure to achieve well-controlled BP within 2 weeks in Scenario A. 	
 • Adjust current or initiate new antihypertensive medication(s). • Titrate antihypertensive medication(s) during the next 2 weeks to achieve well-controlled BP. 	
 • Interrupt trametinib if clinically indicated. • Once BP is well-controlled, restart trametinib reduced by one dose level.^a
(Scenario C) 
 - Symptomatic hypertension or Persistent SBP \geq160 mmHg, or DBP \geq100 mmHg, despite antihypertensive medication and dose reduction of trametinib 	
 • Adjust current or initiate new antihypertensive medication(s). • Titrate antihypertensive medication(s) during the next 2 weeks to achieve well-controlled BP. • Referral to a specialist for further evaluation and follow-up is recommended. 	
 • Interrupt trametinib. • Once BP is well-controlled, restart trametinib reduced by one dose level.^a
(Scenario D) Refractory hypertension unresponsive to above interventions or hypertensive crisis.	Continue follow-up per protocol.	Permanently discontinue trametinib.
a. Escalation of trametinib to previous dose level can be considered if BPs remain well controlled for 4 weeks after restarting of trametinib. Approval from Medical Monitor is required.		

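### Footnote i of the Study Calendar leaves out vital signs after week 12, so late asymptomatic hypertension has no required on-treatment blood pressure reading

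*Combined protocol and SAP*

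**What the plan says.** The calendar in Section 10 gives vital signs their own row, separate from physical exam, weight and performance status. The marks are at Pre-Study, weeks 1, 5 and 9, and Off Treatment. Footnote i, attached to the week 12 column, covers later treatment: "For patients remaining on treatment after week 12, evaluations will include physical exam, weight, performance status", then complete blood count and serum chemistry, at least once per cycle. It does not name vital signs or blood pressure.

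Other monitoring has an explicit long-term interval. The ECHO/MUGA row reads "Every 12 weeks (+/- 14 days) (use same methodology for baseline and follow up", and Section 6.1.7 says "ECHO/MUGAs must be performed in regular intervals outlined in the Study Calendar". Section 11.1 sets response imaging every 8 weeks for 24 weeks and every 12 weeks after that.

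Section 6.1.9 describes how a reading is taken and what to do when it is high. On timing it says "Visits to monitor increased blood pressure can be scheduled independently from the per-protocol visits outlined in the study calendar". Section 5.5 says "treatment may continue for 52 cycles or until one of the following criteria applies", and Section 5.1.1 sets the cycle at 28 days.

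**The concern.** Scenarios A and B of Section 6.1.9 apply to patients without symptoms, who can be found only by taking a reading. Scenario B (systolic pressure of at least 160 mmHg or diastolic of at least 100 mmHg) requires antihypertensive treatment, interruption of trametinib if clinically indicated, and restart one dose level lower. If no reading is required after week 9, a patient whose pressure first rises after week 12 may never trigger these rules. The off-treatment reading comes too late to guide dosing.

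The toxicity is known. In the phase 3 melanoma table in Section 2.2.1.3, hypertension occurred in 15% of trametinib patients at any grade and 12% at grade 3 or 4, against 7% and 3% on chemotherapy. Safety is a secondary objective (Section 1.2) and grade 3-5 rates will be tabulated (Section 13.1). Without scheduled readings, how completely late asymptomatic hypertension is recorded depends on site habit.

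**Working it through.** The plan states no figure on this point. The check is a comparison of texts, followed by simple arithmetic.

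**1. What footnote i carries forward.**

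| Evaluation | Weeks 1, 5, 9 | Footnote i, after week 12 |
|---|---|---|
| Physical exam | yes | yes |
| Weight | yes | yes |
| Performance status | yes | yes |
| Blood count | yes | yes |
| Serum chemistry | yes | yes |
| Vital signs | yes | no |

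**2. Does the physical exam cover it?** Not as the calendar is written. Week 3 has a physical exam mark and no vital signs mark, so the two are treated as different items.

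**3. Is a schedule given elsewhere?** Section 5.4 only allows supportive care for hypertension. Section 6.1.9 gives measurement conditions, definitions and actions, but no frequency. Its extra visits are optional and are for pressure already raised. Moving from Scenario A to B through "Failure to achieve well-controlled BP within 2 weeks in Scenario A" likewise presupposes that an elevation has been found. No routine reading is required between week 9 and the off-treatment visit.

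**4. Size at the maximum duration.**
- Duration: 52 cycles × 4 weeks = 208 weeks.
- After week 12: 208 − 12 = 196 weeks; 196 / 208 = 94%.
- Cycle visits with no listed reading: cycles 4 to 52, so 52 − 3 = 49 of 52.
- Longest scheduled gap: 208 − 9 = 199 weeks.

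**5. Size at shorter durations.** Trametinib exposure in this disease is unknown. As assumptions, take the durations Section 2.1 reports for two other drugs:
- Sorafenib: "The median treatment duration was 124 days with seven patients requiring dose reductions". 124 / 7 = 17.7 weeks. Share after week 12: (17.7 − 12) / 17.7 = 32%. Cycle visits fall at weeks 1, 5, 9, 13 and 17, so 2 of 5 are affected.
- Bevacizumab: "The mean number of cycles received was 17.3 (52 weeks"). Share after week 12: (52 − 12) / 52 = 77%. In 28-day cycles there are 52 / 4 = 13 visits, so 10 of 13 are affected.

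**6. Context on frequency.** At the melanoma rates, 27 × 0.15 = 4.05 and 27 × 0.12 = 3.24, so about 4 patients with any hypertension and 3 with grade 3 or 4 among the 27 fusion-positive patients planned. These are totals over all treatment. The share starting after week 12 is not given.

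**7. With vital signs added.** Scheduled on-treatment readings over a full course rise from 3 to 52. The longest scheduled gap falls from 199 weeks to about 4 weeks, plus the visit window.

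**The case against.** The best reply is that footnote i sets a floor and is not a closed list. It also omits adverse event evaluation and concurrent medications, and nobody would read it as ending either. This is fair, and the footnote's wording does not forbid a reading. However, the calendar draws those two items as continuous lines across the treatment columns, and Section 7.4 separately requires all adverse events to be reported. Vital signs have only discrete visit marks and no such support.

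Second, Section 6.1.9 mentions the calendar's per-protocol visits and defines persistent hypertension over three consecutive visits with blood pressure assessments, so it seems to assume that pressure is taken routinely. It does, but it sets no frequency. After week 12 the calendar does not supply what it assumes.

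Third, the documents state no blood pressure interval that is being breached, and the visit counts describe the schedule, not harm. Both points stand. Onset times are given for skin toxicity and cardiomyopathy but not for hypertension.

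Fourth, the remaining risk is narrow. Symptomatic hypertension and hypertensive crisis would surface by themselves, patients already raised by week 9 are covered by the extra visits, treatment-refractory hypertension is excluded at entry (Section 3.2.10), and many sites will measure pressure anyway. This limits the point without removing it.

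**Conclusion.** The concern holds. Followed as written, the plan requires no blood pressure reading between week 9 and the off-treatment visit, although the dose rules for asymptomatic hypertension need one. The affected share of cycle visits is 49 of 52 at the maximum duration. It is 2 of 5 or 10 of 13 if treatment lasts 124 days or 52 weeks, both assumptions taken from other drugs. The number of patients who would be missed cannot be estimated from the documents.

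The omission looks like a drafting slip. It does not affect the primary endpoint or the two-stage decision rule. It should still be corrected, because it concerns a known toxicity with its own dose-modification section.

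**What to change.** Add vital signs, including blood pressure, to the list in footnote i, at least once per cycle and at the visit that already takes place. The change is a few words and needs no new visit. The burden is one seated reading per cycle visit, plus the second reading that Section 6.1.9 already asks for when the first is in the hypertensive range.
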